### **3.2 Sample Size**

The sample size for the overall study included subjects enrolled in Phase 1b and Phase 2 treated with the same dose regimen. An ORR observed in standard of care for second-line therapies (CCNU) ranged around 5 to 10%. While bevacizumab (Avastin)

demonstrated an ORR > 20%, considerable toxicities were reported. To reject the null hypothesis of ORR ≤ 5% in favor of an alternative hypothesis that the ORR is ≥ 20%, 43 subjects will preserve approximately 88% power to detect the difference at a 0.025 significance level by a 1-sided exact test.

However, the initiation of part 2 of the study was dependent on the results of part 1b. The sample size for part 1b was chosen empirically to be 24 subjects. Furthermore, the sample size for subjects treated with acalabrutinib dose of 200mg BID was 15, while 9 subjects were treated with acalabrutinib dose of 400 mg. The sample size and design changes for part 1b are summarized in the table below:

**Table 1 Phase 1b Sample Size Summary**

Cohort		Phase 1b	
		Scheduled	Overall Enrollment
Cohort 1: ACP-196 200 mg BID	EIAED*	n = 4	n = 0
	Non EIAED	n = 8	n = 15 (7 additional patients)
Cohort 2 ACP-196 400 mg QD	EIAED*	n = 4	n = 1
	Non EIAED	n = 8	n = 8

\*EIAEDs are no longer considered the standard of care for patients with glioblastoma.

This SAP includes Phase 1b safety and efficacy analysis that will be performed on the 24 total subjects in Phase 1b comprising the 9 subjects enrolled in the 400 mg QD cohort and the 15 subjects enrolled in the 200 mg BID cohort (8 subjects enrolled prior to first interim analysis, and an additional 7 subjects completing Phase 1b).

Refer to Amendment 2.0 section 5.1 for more details.

## **4 STUDY ENDPOINTS**

### **4.1 Safety Endpoints**

The safety of acalabrutinib will be characterized by the type, frequency, severity, timing of onset, duration, and relationship to study drug of any treatment-emergent adverse events (TEAEs) or abnormalities of laboratory tests; study drug-related adverse events (AEs), serious adverse events (SAEs), AEs leading to dose modification, dose delay and discontinuation of study treatment.

Refer to Amendment 2.0 section 5.4.1 for more details.

## **4.2 Efficacy Endpoints**

Efficacy will be evaluated based on assessments of tumor response and progression using RANO criteria (Wen 2010).

Efficacy endpoints will include:

- Overall response rate (ORR)
- Duration of response (DOR)
- Progression-free survival (PFS)
- 6-month progression-free survival (PFS-6)
- 4-month progression-free survival (PFS-4)
- OS

## **4.3 Exploratory Endpoints**

## **5 HYPOTHESES AND MULTIPLICITY**

No hypothesis will be tested and no multiplicity adjustments will be made.

## **6 ANALYSIS SETS**

### **6.1 Safety Analysis Set**

All efficacy and safety analysis will be performed using the safety population, which consists of all subjects who receive any amount of acalabrutinib. The analysis of DOR will only include subjects who have achieved objective response.

### **6.2 Pharmacokinetic/Pharmacodynamic Analyses Set(s)**

Pharmacokinetic/Pharmacodynamic evaluable analysis set will be defined by PK and PD group.

## **7 SUBGROUP ANALYSIS**

NA.

## **8 FINAL ANALYSIS AND CLINICAL STUDY REPORT**

Planned final analysis will be conducted once last subject exits study, or sponsor decides to close the study, whichever occurs earlier.

## **9 MISSING VALUES**

No imputation of values for missing data will be performed except for missing or partial

dates according to prespecified, conservative imputation rules. The details of imputation rules for partial or missing dates are listed in [Appendix 12.2](#).

## **10 STATISTICAL METHODS OF ANALYSIS**

### **10.1 General Principles**

Descriptive statistics [including sample size, group means, standard deviations, medians, minimum and maximum for continuous variables and sample size, frequency, proportions and confidence intervals (CIs) for discrete variables] will be used to summarize will be used to summarize data as appropriate.

Calculation of time to event or duration of event endpoints will be based on the study day of the event or censoring date rather than visit number or visit label. Missing efficacy or safety data will not be imputed unless otherwise specified.

The following rules will be used for the days to months/years conversion:

- 1 month= 30.4375 days;
- 1 year= 365.25 days.

All summaries will be presented by treatment cohort.

### **10.2 Subject Accountability**

The number of subjects enrolled by site, country and region (US and ex-US) will be presented. Subject disposition will be summarized for all enrolled subjects including the following information:

- Proportion of subjects who received study drug
- Proportion of subjects with study drug discontinuation and primary reason for study drug discontinuation
- Proportion of subjects discontinuing study and reasons for study discontinuation
- Time on study

### **10.3 Important Protocol Deviations**

Important Protocol Deviations (IPDs) categories are defined and managed by the study team during the IPD reviews throughout the study before database lock. The final IPD list for each study is used to produce the summary of IPDs table and the listing of subjects with IPDs, respectively.

### **10.4 Demographic and Baseline Characteristics**

Summaries of demographic characteristics will be presented for age, age category (< 65, ≥ 65), gender, race, ethnicity, and geographic region.

Baseline characteristics will be presented for Eastern Cooperative Oncology Group (ECOG) performance status, disease stage, tumor grade, number of prior anticancer therapies.

## **10.5 Treatment and Medications**

### **10.5.1 Prior Anticancer Therapies**

Summary statistics will be presented for prior anticancer regimens (might include multiple therapies) and prior cancer-related surgery. The number of lines and type of prior therapy will be summarized.

### **10.5.2 Concomitant Medications**

Concomitant medications will be coded and tabulated according to the World Health Organization (WHO) Drug Dictionary (WHODRUG).

### **10.5.3 Exposure to Investigational Product**

The number of subjects who received at least one dose of acalabrutinib, duration of exposure, average daily dose, and relative dose intensity will be summarized by treatment cohort.

Exposure parameters are defined in more detail in [Appendix 12.1](#).

## **10.6 Safety Analyses**

All safety analysis will be performed using the safety analysis set.

### **10.6.1 Adverse Events**

The Medical Dictionary for Regulatory Activities (MedDRA v20.1 or later) will be used to code all AEs to a system organ class and a preferred term. The severity of the AE will be assessed by National Cancer Institute (NCI) Common Terminology Criteria for Adverse Events (CTCAE) Version 4.03. Study drug-related AEs are those assessed by investigator as related.

All AE tables will be summarized by treatment cohort.

TEAEs are defined as those events that occur or worsen on or after the first dose of study drug (acalabrutinib), through the treatment phase, and within 30 days following the last dose of acalabrutinib.

TEAEs will be summarized by system organ class (SOC) and preferred terms (PTs) as well as preferred terms only in descending order of frequency, by CTCAE severity grade.

Drug-related TEAEs, treatment-emergent serious adverse events (TESAEs), TEAEs leading to study drug discontinuation or dose modifications or dose delay will be summarized by PTs in descending order of frequency and by CTCAE severity grade.

Death information is reported in the study exit case report form (CRF) and death information CRF for all deaths. Incidences of deaths are to be reported, along with the primary cause of death.

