3.9.4 Hepatitis B Virus Reactivation

Serious or life-threatening reactivation of viral hepatitis may occur in subjects treated with BTK inhibitor ([de Jésus Ngoma 2015](#)). Therefore, subjects who are anti-HBc positive, or have a known history of hepatitis B virus (HBV) infection, should be monitored every 3 months with a quantitative PCR test for HBV DNA. Regular monitoring (every 3 months) should continue until 12 months after last dose of acalabrutinib. Any subject with a rising viral load (above lower limit of detection) should discontinue acalabrutinib and have antiviral therapy instituted and a consultation with a physician with expertise in managing hepatitis B. Insufficient data exist regarding the safety of resuming acalabrutinib in subjects who develop HBV reactivation.

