4.3 TREATMENT TERMINATION AND SAFETY FOLLOW-UP VISITS

A TT visit is required for safety assessments for any subjects who permanently discontinue study drug for any reason (except for death, lost to follow-up, or withdrawal of consent), including disease progression. The TT visit should be scheduled within 7 days of the last dose of study drug, if possible, and is not required for subjects who discontinue from the study treatment within 10 days of a scheduled study visit or if the TT visit would be performed within 14 days of the SFU visit.

In addition to the TT visit, each subject should be followed until the SFU visit at 30 (+7) days after his or her last dose of study drug to monitor for resolution or progression of AEs and to document the occurrence of any new events, regardless of whether the subject receives a new anticancer therapy or demonstrates disease progression within this timeframe. Subjects who withdraw consent for study treatment should still be encouraged to complete the SFU assessments, but these assessments cannot be mandated if subject consent for further study participation is withdrawn. If the TT visit and the SFU visit coincide, then these can be combined into 1 visit. The Schedule of Assessments ([Appendix 1](#)) describes the procedures required for the TT and SFU visits.

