5.4 ENDPOINT DATA ANALYSIS

5.4.1 Safety Endpoint

Verbatim descriptions of AEs will be mapped according to the MedDRA thesaurus terms and graded according to the National Cancer Institute (NCI) CTCAE, v4.03 or higher. Extent of exposure to study drug, all AEs, SAEs, non-SAEs leading to study drug discontinuation, and study drug-related AEs will be summarized. The frequency of AEs will be summarized by system organ class and preferred terms according to MedDRA,

as well as per severity per NCI CTCAE grade. Only treatment-emergent AEs will be summarized. For events with varying severity, the worst reported grade will be used.

Laboratory abnormalities will be defined based on laboratory normal ranges (universal normal ranges if central laboratory) and will be summarized by visit. Selected laboratory parameters may be analyzed with shift tables and summaries of changes from baseline to worst post-treatment value. Figures of changes in laboratory parameters over time may be generated, as appropriate, for certain labs.

Change from baseline in vital sign assessments will be tabulated and summarized.

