6.2.1 Adverse Event Reporting Period

After the signing of the ICF *and prior to the first dose of study drug*, all SAEs must be reported. After the first dose of study drug, all AEs/SAEs, irrespective of attribution of causality, must be reported.

All AEs will be reported until 30 days after the last dose of study drug or the start of new anticancer therapy (whichever comes first). After this period, investigators should report SAEs or other AEs of concern that are believed to be related to prior treatment with study drug.

All SAEs that occur during the reporting period should be followed to resolution or until the investigator assesses the subject as stable or until the subject is lost to follow-up or withdraws consent. Resolution/stable means the subject has returned to baseline state of health or the investigator does not expect any further improvement or worsening of the event.

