#### **10.6.3 Laboratory Test Results**

Laboratory data up to 30 days after last dose or the safety follow-up visit date, whichever is later, will be reported in International System of Units (SI) units. Applicable laboratory results will be graded according to CTCAE Version 4.03. For each laboratory parameter, the baseline laboratory value/grade is defined as the last laboratory value/grade collected on or prior to the date of the first dose of study drug. Treatment-emergent laboratory abnormalities for selected parameters will be summarized.

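### Non-fatal drug-related events starting more than 30 days after last dose, and HBV DNA results after the safety follow-up visit, have no specified table or listing

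*SAP*

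**What the plan says.** **Collection.** Protocol 6.2.1 has all AEs reported until 30 days after last dose or the start of new anticancer therapy, whichever is first. It then adds: "After this period, investigators should report SAEs or other AEs of concern that are believed to be related to prior treatment with study drug". No end date is given. A footnote to the Appendix 1 schedule likewise requires related SAEs after the reporting period.

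For hepatitis B, protocol 3.9.4 says "subjects who are anti-HBc positive, or have a known history of hepatitis B virus (HBV) infection, should be monitored every 3 months" by quantitative PCR, and "Regular monitoring (every 3 months) should continue until 12 months after last dose of acalabrutinib". Section 4.1.15 and Appendix 1 repeat this; the schedule marks the test every 3 months in both post-treatment follow-up columns.

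**Reporting.** SAP 10.6.1 ends the treatment-emergent period with the words "through the treatment phase, and within 30 days following the last dose of acalabrutinib". Besides the overall TEAE tables, it names these: "Drug-related TEAEs, treatment-emergent serious adverse events (TESAEs), TEAEs leading to study drug discontinuation or dose modifications or dose delay will be summarized". Protocol 5.4.1 states the restriction outright: "Only treatment-emergent AEs will be summarized". For laboratory results, SAP 10.6.3 says: "Laboratory data up to 30 days after last dose or the safety follow-up visit date, whichever is later, will be reported". The SFU visit is set by protocol 4.3: "each subject should be followed until the SFU visit at 30 (+7) days after his or her last dose of study drug".

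**Two outputs without a stated limit.** SAP 10.6.1 reports all deaths with primary cause. SAP 10.6.2 summarises ECIs and gives no time window. The categories in SAP 12.5.1 include the whole infections system organ class and second primary malignancies.

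**The concern.** Characterising safety is a primary objective. The protocol extends surveillance past day 30 for events judged related to the drug, and for up to a year for HBV reactivation, which it describes as potentially serious or life-threatening. The reporting rules stop at about one month.

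These are stated rules, not silence. An analyst who follows them leaves a non-fatal, investigator-attributed event with onset on day 31 or later out of every AE table named in SAP 10.6.1. HBV DNA results after the SFU visit fall outside the laboratory output. SAP 4.1 lists study drug-related AEs and SAEs as safety endpoints without repeating the treatment-emergent limit, but 10.6.1 tabulates only their treatment-emergent versions. In cohorts of 15 and 9, one such event would visibly change a reported incidence.

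**Working it through.** The plan states no figure on this point, so there is none to reproduce. The check compares windows, using the SAP's conversion of 30.4375 days per month (SAP 10.1).

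**1. AE window.** The TEAE period ends at last dose + 30 days (SAP 10.6.1). Related SAEs and AEs of concern are collected beyond that with no end date (protocol 6.2.1). Every such event with a known onset on day 31 or later is outside all the AE tables named.

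The date rules in SAP 12.2 show that such onsets were foreseen. A partial AE start date imputed to later in the same month as last dose + 30 is moved back to last dose + 30. A late event with a missing day can therefore be counted, while the same event with a complete date is not.

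**2. Laboratory window against HBV monitoring.** The window closes between day 30 and day 37 (the SFU visit at 30 +7). Monitoring runs to 12 × 30.4375 = 365.25 days after last dose.

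| Laboratory window closes | Monitoring days outside | Share outside |
|---|---|---|
| Day 30 | 365.25 − 30 = 335.25 | 335.25 / 365.25 = 91.8% |
| Day 37 | 365.25 − 37 = 328.25 | 328.25 / 365.25 = 89.9% |

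**3. How many HBV DNA tests fall outside.** This depends on where the 3-month clock starts.

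- Counted from last dose: tests fall at 3, 6, 9 and 12 × 30.4375 = about days 91, 183, 274 and 365. All four are outside.
- Counted from screening, as protocol 4.1.15 and Appendix 1 can be read: one test can fall inside the window by chance, leaving three of four outside. If last dose falls at random within a 91.3-day cycle (an assumption), that chance is 30/91.3 to 37/91.3, or about 33% to 41%.

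**4. Size of one omission (illustration, not an estimate).** Cohort sizes are 15 and 9 (SAP Table 1).

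- 200 mg BID: 1/15 = 6.7% (exact 95% CI 0.2% to 31.9%), shown instead as 0/15.
- 400 mg QD: 1/9 = 11.1%, shown instead as 0/9.

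**5. What the other outputs would catch.**

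| Late event | Named AE tables | Death summary | ECI summary |
|---|---|---|---|
| Fatal | No | Yes, with cause | Depends on category and window |
| Non-fatal infection (including HBV reactivation or PML, which protocol 3.9.2 lists under infections) | No | No | Possible; window not stated |
| Non-fatal second primary malignancy | No | No | Possible; window not stated |
| Other non-fatal related SAE outside the ECI categories | No | No | No |
| HBV DNA value after the SFU visit | Not applicable | Not applicable | No; not an AE |

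**The case against.** A reader might infer that late drug-related harms appear in no planned safety output at all. The documents do not support that. Deaths are reported whatever their timing. The ECI summary carries no cut-off of its own, and its categories reach the harms of most interest. Against this, protocol 5.4.1 limits AE summaries to treatment-emergent events without exception, and ECIs are AEs, so the ECI summary may be cut as well. The fair statement is that its window is undefined.

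A reader might also infer that the SAP departs from the protocol. For AEs it does not: protocol 5.4.1 sets the same restriction, so the gap is shared. Only the laboratory cut-off is the SAP's own.

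There is also a sound reason for the restriction. Ascertainment is complete up to the end of the reporting period and limited to related events afterwards. Mixing the two in one incidence table would mislead. That argues for a separate display, not for none.

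Oversight continues elsewhere. SAEs are reported within 24 hours (protocol 6.2.5), and the Safety Review Committee and Scientific Advisory Committee review AEs and SAEs at least every 3 months (protocol 3.12). This protects subjects but does not put the events in the study report. With 24 subjects, late events could be described individually in the report, but the plan does not call for it.

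Three limits on the HBV part stand. Monitoring covers only subjects who are anti-HBc positive or have a known HBV history, and that number is not given. Patients with positive surface antigen or HBV PCR are excluded at entry. No visible text shows that results to month 12 enter the study database, since testing may be local and is described as part of individual management.

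**Conclusion.** The point holds, as a minor reporting gap. Non-fatal related SAEs and AEs of concern with onset after last dose + 30 days are collected, but they fall outside every AE table named in SAP 10.6.1 and are excluded by protocol 5.4.1. HBV DNA results after the SFU visit fall outside SAP 10.6.3, which leaves roughly 90% to 92% of the 12-month monitoring period uncovered. Three or four of the four quarterly tests are outside, depending on the clock.

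The effect on results cannot be estimated from the documents and may be nil: it is zero if no such event occurred and no subject was HBV-monitored. One omitted event would be 6.7 percentage points in one cohort or 11.1 in the other. No efficacy conclusion is touched, and SAP section 5 plans no hypothesis test. The final analysis follows the last subject's exit or closure by the sponsor, whichever is earlier (SAP section 8), so late data can be available but early closure could truncate them.

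**What to change.** 1. **SAP 10.6.1:** keep the TEAE tables unchanged. Add one by-cohort table with a listing of AEs and SAEs assessed as related with onset after last dose + 30 days. Label it *post-treatment, related* and do not pool it with TEAE rates.
2. **SAP 10.6.2 and 12.5:** state the time window of the ECI summary and show post-treatment related ECIs separately.
3. **SAP 10.6.3:** exempt HBV DNA from the cut-off. For monitored subjects, list all results captured in the study database to 12 months after last dose, and state how many subjects were monitored.
4. **Protocol 5.4.1:** align the sentence that limits summaries to treatment-emergent AEs, for example: *Treatment-emergent AEs will be summarized; drug-related AEs reported after the treatment-emergent period will be presented separately.*

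The cost is SAP wording, one table, one event listing and one HBV DNA listing. No new data collection is proposed, and no monitoring or treatment rule changes. The remaining limitation is that ascertainment after the reporting period covers related events only, so the new table gives counts of reported related events, not an incidence comparable with the TEAE tables. A footnote should say so.

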#### **10.6.2 Events of Clinical Interest**

Broader categories of Events of Clinical Interest (ECI) identified for acalabrutinib will be summarized. The definitions of these categories for safety analysis are part of [Appendix 12.5.1](#) and [Appendix 12.5.2](#).

#### **10.6.3 Laboratory Test Results**

Laboratory data up to 30 days after last dose or the safety follow-up visit date, whichever is later, will be reported in International System of Units (SI) units. Applicable laboratory results will be graded according to CTCAE Version 4.03. For each laboratory parameter, the baseline laboratory value/grade is defined as the last laboratory value/grade collected on or prior to the date of the first dose of study drug. Treatment-emergent laboratory abnormalities for selected parameters will be summarized.

#### **10.6.4 Vital Signs**

Body temperature, heart rate (beats/min), systolic blood pressure (mmHg), diastolic blood pressure (mmHg), respiratory rate (breaths/min), and weight will be collected for each study as scheduled in Amendment 2 Appendix 1. Schedule of Assessments. For each parameter, summary statistics (mean, standard deviation, median, and range) will be produced for baseline, maximum, and minimum value.

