4.1.7 Physical Examination, Vital Signs, Height, and Weight

The screening physical examination will include, at a minimum, the general appearance of the subject, height (screening only) and weight, and examination of the skin, eyes,

ears, nose, throat, lungs, heart, abdomen, extremities, musculoskeletal system, nervous system, and lymphatic system.

Symptom-directed physical exams will be done during the treatment period and at the treatment termination (TT) and safety follow-up (SFU) visits.

Vital signs (blood pressure, heart rate, and body temperature) will be assessed after the subject has rested in the sitting position.

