## **1 INTRODUCTION**

The purpose of this statistical analysis plan (SAP) is to provide details of the statistical analyses that have been outlined within the protocol Amendment 2.0, 21 March 2017 for [REDACTED] ACE-ST-209 (Glioblastoma multiforme, GBM). The scope of this plan includes the final analysis that are planned and will be executed by the Biometrics department or designee. Any changes to the methods described in the final SAP will be documented in the clinical study report (CSR).

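### SAP 10.6.4 omits the protocol's change-from-baseline summary of vital signs and specifies only baseline, maximum and minimum, which move apart by chance alone

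*SAP*

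**What the plan says.** Protocol 5.4.1 (Safety Endpoint) commits to a change score: "Change from baseline in vital sign assessments will be tabulated and summarized". It does not give the visits at which the change is to be shown.

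SAP 10.6.4 (Vital Signs) plans the mean, standard deviation, median and range, and says that these "will be produced for baseline, maximum, and minimum value". It specifies no change score, by-visit table, shift table or threshold. It does not say which readings enter the maximum and minimum, or whether baseline is among them. A baseline rule is given in SAP 10.6.3, but for laboratory data only: "For each laboratory parameter, the baseline laboratory value/grade is defined as the last laboratory value/grade collected on or prior" to the first dose.

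SAP 1 describes its purpose as to "provide details of the statistical analyses that have been outlined within the protocol Amendment 2.0, 21 March 2017", and no departure from the protocol is declared for vital signs. SAP 4.1 (Safety Endpoints) sends the reader to protocol section 5.4.1 for more detail. SAP 10.1 adds: "All summaries will be presented by treatment cohort". The cohorts are "the 9 subjects enrolled in the 400 mg QD cohort and the 15 subjects enrolled in the 200 mg BID cohort" (text after SAP Table 1).

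SAP 10.6.4 also lists respiratory rate. Protocol 4.1.7 does not: "Vital signs (blood pressure, heart rate, and body temperature) will be assessed" once the subject has rested.

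**The concern.** The protocol names one summary and the SAP specifies another, without comment. The SAP's choice also has a built-in direction. A baseline value is one reading, whereas a maximum is the largest of several. The largest of several readings tends to exceed a single reading from the same subject even if blood pressure, pulse and temperature never change, and the smallest tends to fall below it. Set beside baseline, the two columns suggest that treatment both raised and lowered the measurement.

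Characterising safety is a primary objective, and the study has no control arm in which the same artefact would appear and could be recognised. The gap also widens with the number of readings, so it depends on how long a subject stays on study.

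**Working it through.** The documents give no figure for vital signs, so there is nothing to reproduce. The check is how far the planned columns would separate with no drug effect.

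**Inputs**

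- Number of post-baseline visits, *k*, counted from protocol Appendix 1 with Cycle 1 Day 1 as baseline. Cycle 1 adds Days 8, 15 and 22, so *k* = 3. Cycle 2 adds Days 1, 8, 15 and 22, so *k* = 7. Cycles 3 and 4 add Days 1 and 15 each, so *k* = 11. The treatment termination and safety follow-up visits would make it 13.
- Within-subject SD of a reading: not in the documents. Results are given in SD units, then for systolic pressure under an assumed 5 to 12 mmHg.
- Correlation between visits: not in the documents. First-order autocorrelation of 0, 0.3 and 0.6 was tried.

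**Formula.** With independent normal readings and no drug effect, expected maximum minus baseline is SD × E(k), where E(k) = ∫ x · k · φ(x) · Φ(x)^(k−1) dx. The minimum gives the same figure with a minus sign. The correlated cases come from a simulation of 200,000 subjects.

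**Results: maximum over post-baseline visits minus baseline, in SD units**

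| k | independent | autocorrelation 0.3 | autocorrelation 0.6 |
|---|---|---|---|
| 3 | 0.85 | 0.74 | 0.58 |
| 7 | 1.35 | 1.27 | 1.08 |
| 11 | 1.59 | 1.52 | 1.34 |
| 13 | 1.67 | 1.60 | 1.44 |

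With *k* = 1 the expected gap is zero. If baseline is counted among the readings, the gap is larger: 1.43 SD at *k* = 7 and 1.63 SD at *k* = 11 (independent visits).

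**In mmHg, independent visits**

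- *k* = 7: 1.352 × 5 = 6.8; 1.352 × 8 = 10.8; 1.352 × 12 = 16.2.
- *k* = 11: 1.586 × 5 = 7.9; 1.586 × 8 = 12.7; 1.586 × 12 = 19.0.
- Difference between 11 and 7 visits: 1.586 − 1.352 = 0.234 SD, or 1.9 mmHg at SD 8 and 2.8 mmHg at SD 12.

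**In a cohort of 15.** With independent visits and no effect, the mean maximum exceeded the mean baseline in 99.6% of 20,000 simulated cohorts at *k* = 3, and in all of them at *k* = 7 and *k* = 11.

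**With a real shift.** For a true rise of 5 mmHg, SD 8 and *k* = 7, the maximum would sit at 5 + 10.8 = +15.8 mmHg from baseline and the minimum at 5 − 10.8 = −5.8 mmHg. The midpoint of the two is still +5, but each column taken alone misstates the size, and the minimum misstates the direction.

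**With change from baseline at a fixed visit.** In the same simulations with no effect, the mean change at the last visit was within 0.008 SD of zero in every setting.

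**The case against.** The strongest reply is that nothing has been dropped. SAP 4.1 refers to section 5.4.1, which in the supplied protocol contains the change-from-baseline sentence, and the SAP nowhere withdraws it. This stands: a reader might infer that the SAP replaced the protocol analysis, but the documents show only an omission from the section where a programmer would look for the specification.

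Second, the protocol does not require a by-visit display for vital signs. Change from baseline to the maximum would satisfy its sentence literally and carry the same artefact; 5.4.1 itself uses change to the worst value for laboratory data. This also stands. The by-visit form is recommended because it avoids the artefact, not because the protocol states it.

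Third, a reader might infer that a change score would reveal a drug effect on blood pressure. It would not do so by itself. There is no comparator, corticosteroids are permitted, and subjects leave treatment at progression, so a mean change mixes several causes. The zero in the simulation assumes no dropout and no co-medication effect.

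Fourth, a reader might infer that a hypertension signal would be lost. SAP 12.5.1 captures hypertension from coded adverse events, independently of this table.

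Fifth, the consequences are limited. SAP 5 tests no hypothesis, no decision rule uses vital signs, and Phase 2 was not opened. SAP 10.6.4 plans no subtraction of columns, so the false rise arises only when a reader compares them. Putting baseline beside the extremes does invite that comparison, however.

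**Conclusion.** The concern holds in a limited form. SAP 10.6.4 omits the change score that protocol 5.4.1 promises, and the summaries it does specify separate from baseline by chance: about 1.35 SD with 7 visits and 1.59 SD with 11 if visits are independent, and about 1.1 and 1.3 SD with autocorrelation 0.6. The direction of the artefact needs only more than one post-baseline reading. Its size depends on the visit count and the correlation, and the mmHg figures also rest on an assumed SD. The main figures assume that maximum and minimum are taken over post-baseline visits, which the SAP does not say.

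Because the gap grows with visits, a reader might infer that the two cohorts will be distorted unequally. That would follow if they differed in time on study, but no document shows that they do.

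This is a minor reporting fault that is worth correcting because it is cheap to correct. It does not affect the efficacy analysis. The respiratory-rate mismatch is clerical: the SAP cites the Amendment 2 schedule, which was not supplied, and the supplied protocol is a later version.

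**What to change.** In SAP 10.6.4:

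1. Add the change-from-baseline summary from protocol 5.4.1, preferably at each scheduled visit. SAP 10.1 already puts all summaries by cohort.
2. Define the vital-sign baseline, for example by extending the laboratory rule in SAP 10.6.3, and define the on-treatment window for post-baseline readings.
3. Keep maximum and minimum as a supplementary display for spotting extremes, and state whether baseline is included in them.
4. Reconcile respiratory rate with protocol 4.1.7, which does not list it.

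If the sponsor prefers not to produce the change score, the SAP should state and justify the departure from protocol 5.4.1.

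The cost is a few lines of SAP text and one more table from data already collected. The downside is small numbers at later visits, with 15 and 9 subjects at the start, so the count contributing at each visit should be shown.
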